EuroQol Group 5-Dimension Self-Report Questionnaire (EQ-5D). EQ-5D [15] is a validated instrument that measures health-related quality of life in five dimensions: mobility, self-care, usual activities, pain/discomfort, and anxiety/depression. It also includes the EQ-VAS which is used to measure the individual's global self-rated health status. Subjects will complete an EQ-5D form at baseline and at each follow-up visit up to 36 months.

International Index of Erectile Function Questionnaire (IIEF-15). IIEF-15 [16] is a validated, fifteen-item questionnaire designed to diagnose the presence and severity of erectile dysfunction. Subjects will complete an IIEF-15 form at baseline and at each follow-up visit up to 60 months.

Male Sexual Health Questionnaire to assess Ejaculatory Dysfunction (MSHQ-EjD). MSHQ-EjD [17] is a validated, four-item questionnaire that assesses ejaculatory function and related distress or bother. Subjects will complete a MSHQ-EjD form at baseline and at each clinic visit up to 60 months.

Incontinence Severity Index (ISI). ISI [18] is a validated means of assessing incontinence and will assist in isolating *de novo* incontinence rather than preexisting incontinence secondary to Bladder Outlet Obstruction.

WPAI: US: is a validated six-item questionnaire that assess the effect of urinary symptoms on a subject's ability to work and perform regular activities.

Concomitant Medications. All medications will be recorded on a rolling log up to 36 months follow-up visit. All urological AE related medication and BPH related medication will be recorded for 48 and 60 months follow-up phone call/visit.

Concomitant Procedures. All urologic procedures that occur during follow-up will be recorded on a rolling log up to 36 months follow-up visit.

2.30 Adverse events.

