[†]This includes the following: persistent ejaculatory dysfunction, erectile dysfunction or urinary incontinence and urinary retention requiring re-catheterization after 3 days post-procedure. Note that bladder catheterization itself is considered a Clavien-Dindo Grade 1 event.

2.30.2 48 & 60 months AE collection

For the 48-month phone call and 60-month follow-up visit, only urological adverse event data will be recorded in the study-specific Electronic Data Capturing system. Study investigators have the responsibility to report all type of AEs to the respective IRB/IEC per each institution's requirement.

AE information (start and stop date, description of event, and severity) will be assessed and recorded on CRFs. Events that meet the criteria of an SAE in **Table 3** must be reported to the Sponsor within 24 hours of the site's awareness.

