- Pain & dysuria score at post-op, 7, 30 days, and 3 months
- EQ-5D at baseline, and 7 days, 1, 3, 6, 12, 24 and 36 months
- ISI at baseline, at post-op, 7 days, 1, 3, and 6 months
- IIEF-15 at baseline, and 7 days, 1, 3, 6, 12, 24, 36 months and 60 months
- MSHQ-EjD at baseline, 7 days, 1, 3, 6, 12, 24, 36 months and 60 months
- WPAI:US at baseline, 7 days, 1, 3, 6, 12, 24 and 36 months
- Pdet@Qmax at baseline and 6 months
- Change in categorization, by treatment group, of subjects from obstructed to unobstructed or unobstructed to obstructed. The determination of “obstructed” and “unobstructed” is based on Chapple [20]
- Use of cautery immediately post Aquablation. Cautery use will be assessed as minutes from cautery start to stop and total amount of “on time”.
- Number of subjects in whom re-catheterization was needed between discharge after the index procedure and month 3. Re-catheterization is defined as the need to place a urinary catheter in the bladder for symptoms related to BPH. This excludes re-catheterization for study purposes or for purposes unrelated to LUTS.
- Amount of irrigation fluid used intraoperatively (liters)
- Number of subjects in whom postoperative irrigation started
- Amount of Fluid used postoperatively (liters)
- Duration of postoperative irrigation (hours)
- Subset analyses of the following variables by treatment and baseline IPSS scores of < 20 and ≥ 20 , as well as by treatment and baseline prostate size of $< 45g$ and $\geq 45g$:
 - IPSS score at baselines, and 7 days, 1, 3, 6, 12, 24 and 36 months
 - IPSS-QoL at baseline, and 7 days, 1, 3, 6, 12, 24 and 36 months
 - Qmax at baseline, 1, 3, 6, 12, 24 and 36 months
 - PVR at baseline, 1, 3, 6, 12, 24 and 36 months
 - Operative time (minutes)
 - Resection time (minutes)
- Evaluation of proportion of subjects with Clavien-Dindo classification of Grade 2 or higher or any Grade 1 with persistent disability (e.g. ejaculatory disorder or erectile dysfunction) at 30 days, 3 months, 6 months, and 1 year

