4.5.3 Safety

The safety analysis population includes all randomized subjects. Secondary safety endpoints including the summary of adverse events in the trial will be analyzed using this analysis population, divided into groups according to actual treatment received.

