8 DEFINITIONS

Hematuria Categorized as an Adverse Event – Subjects who require any of the following:

- Extended catheterization beyond 3 days
- Repeat catheterization beyond three days post treatment
- Extended Hospitalization – per hospital standard of care (Serious Adverse Event)
- Blood transfusion (Serious Adverse Event)

Non-Reportable Events - Mild to moderate symptoms that are typically associated with the usual post-operative course including but not limited to dysuria, decreased urinary flow, gross hematuria within 7 days post treatment.

Post Treatment Catheterization Rate – The proportion of participants who are catheterized within 3 days following treatment with the AQUABEAM System.

Urinary Retention Adverse Event – Subjects who present beyond three days post treatment and are unable to void requiring catheterization to resolve their symptoms.

Urinary Incontinence – Subjects who didn't require incontinence pads prior to Aquablation treatment and require more than 1 incontinence pad per day post-treatment.

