## 7 Additional Endpoint Assessments

The following additional endpoints, evaluated using the PP cohort, are pre-specified but are not intended to support product labeling. Comparisons of proportions described below will be done using methods similar to those described for the reoperation/reintervention secondary endpoint. Comparisons of continuous variables will use a t test unless otherwise described. Testing of continuous variables will examine superiority, and in some cases, non-inferiority. Superiority tests will be 2-sided ( $\alpha=0.05$ ). Non-inferiority tests will be one-sided ( $\alpha=0.025$ ).

1. Proportion of subjects with Clavien-Dindo classification of Grade 2 or higher or any Grade 1 with persistent disability (e.g. ejaculatory disorder or erectile dysfunction) at 30 days, 6 months, and 1 year. 6-month and 1-year calculations will be performed only when full datasets are available. A 10% NIM will be used.

---

\* According to personal communication [name], creator of MSHQ, no published MCID for MSHQ exists.

2. Evaluation of the proportion of subjects with dysuria through the day 30 visit. Dysuria is defined as burning sensation while urinating of at least “about ½ the time” on the dysuria questionnaire. An additional comparison using proportion odds logistic regression will be performed. A 15% NIM will be used.
3. Duration of bladder catheterization (i.e., intraoperative catheter placement to removal prior to discharge) after the assigned study procedure. Duration will be compared with a t test. An NIM of ½ a day will be used.
4. Change in hemoglobin (gm/dl) (i.e., laboratory test) at discharge from baseline.
5. Reoperation or Re-intervention within 30 days, 12 months, 24 months and 36 months. For the 30-day time point, proportions will be compared with a 10% NIM. For longer time points, due to the expectation of study withdrawal, Kaplan-Meier survival analysis will be performed and a log rank test calculated.
6. Changes in the proportion of subjects using medications for BPH symptoms at month 6. Two analyses will be done. 1) an analysis of the proportion of subjects who increased doses of BPH medications or started a new BPH medication, and 2) the proportion who were able to decrease or stop doses of BPH medications. Relevant medications include alpha blockers, prostaglandin inhibitors, and phosphodiesterase inhibitors. A 10% NIM will be used.

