7. IPSS change score during follow-up (1 week, 1, 3, 6, 12, 24 and 36 months). Repeated measures analysis of variance (RMANOVA) will be used, with additional models that include baseline IPSS as a covariate. This analysis accounts for all available measurements and correlation of measurements within subjects. The mean differences across groups will be determined and the confidence limits from the regression model compared with the study-specific NIM. A treatment × time interaction will be explored as well. The purpose of this analysis is to evaluate whether the IPSS change score across all time points is non-inferior in A compared to T. The same NIM will be used as described for the primary effectiveness endpoint. If non-inferiority is shown, superiority will be tested. All available time points will be used up to month 36.
8. IPSS-QoL change scores (1 week, 1, 3, 6, 12, 24 and 36 months). A similar method as that with IPSS change score will be used and a 1-point NIM will be assumed.
9. Qmax change scores at 1, 3, 6, 12, 24 and 36 months. RMANOVA will be used.
10. PVR change scores at 1, 3, 6, 12, 24 and 36 months. RMANOVA will be used.
11. Proportion of subjects with device- or procedure-related adverse event. Proportions compared as described for primary safety endpoint.
12. Pelvic pain intensity level, population mean and change score mean, measured on a 0-10 numeric rating scale. Population score distributions will be compared with a Wilcoxon signed rank test. Change scores will be compared with a Wilcoxon test or t test. A non-inferiority margin of 2 points will be used.

13. EQ-5D time trade-off index (TTO) change scores during follow-up (7 days, and 1, 3, 6, 12, 24 and 36 months). TTO will be calculated using study data combined with available country-specific norms. RMANOVA will be used.
14. ISI at baseline, at post-op, 7 days, 1, 3, and 6 months. RMANOVA will be used.
15. IIEF-15 at baseline, and 7 days, 1, 3, 6, 12, 24 and 36 months. RMANOVA will be used.
16. MSHQ-EjD at baseline, 7 days, 1, 3, 6, 12, 24 and 36 months. RMANOVA will be used.
17. WPAI:US at baseline, 7 days, 1, 3, 6, 12, 24 and 36 months. Specifically, among those subjects who are currently working, the number of hours missed due to urinary symptoms will be compared. Given a large expected number of zeroes, a non-distributional method such as Wilcoxon's test will be used.
18. Pdet@Qmax at baseline and 6 months. This continuous outcome will be evaluated with a t test.

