19. Change in categorization of subjects from obstructed to unobstructed or unobstructed to obstructed at month 6 in those subjects in whom urodynamics was performed. (Urodynamics is an optional test.) The determination of "obstructed" and "unobstructed" is based on urodynamics values and Chapple. Specifically, AG (Abrams-Griffith) number is calculated as  $AG = Pdet@Qmax - 2 * Qmax$ . AG is interpreted as:
  - If  $AG \geq 40$ : obstructed
  - If  $AG < 20$ : not obstructed
  - If  $20 \leq AG < 40$ : calculate slope =  $(Pdet@Qmax - Pvoid0) / Qmax$ . If slope  $> 2$ , obstructed, else unobstructed.

Changes from baseline to follow-up within a treatment group will be calculated with a McNemar's test. Conditional odds ratio will be calculated according to Suzuki.
20. Use of cautery immediately post Aquablation. The proportion in which cautery was used and the distribution of cautery time will be calculated. Cautery use will be assessed as minutes from cautery start to stop and total amount of "on time".
21. Proportion of subjects in whom re-catheterization was needed between discharge after the index procedure and month 3. Re-catheterization is defined as the need to place a urinary catheter in the bladder for symptoms related to BPH. This excludes re-catheterization for study purposes or for purposes unrelated to LUTS.
22. Amount of irrigation fluid used intraoperatively (liters). A t test or Wilcoxon's test will be used to evaluate mean differences.
23. Proportion of subjects in whom postoperative bladder irrigation was started.
24. Prostate size reduction from baseline to 3 months as measured TRUS. A t test will be used for the comparison.
25. Relationship between prostate size reduction and change in various measurements (IPSS, etc.).

26. Relationship between prostate size and procedure or resection times. It is expected that procedure times will be related to prostate size in T but not A. Linear models will be run for each treatment group. In addition, a linear model will be run for all subjects that includes an interaction term.

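### The only planned ISI analysis is a repeated-measures comparison of the score in the whole PP cohort; it mixes relief of old leakage with new leakage and does not show how many men newly leak in each arm

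*SAP*

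**What the plan says.** Protocol section 2.29 describes the ISI as a validated measure of incontinence that "will assist in isolating *de novo* incontinence rather than preexisting incontinence secondary to Bladder Outlet Obstruction". Protocol section 3.3 lists only the visits ("ISI at baseline, at post-op, 7 days, 1, 3, and 6 months") and sets no cut-off, contrast or definition of new incontinence.

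SAP section 7, item 14, is the only ISI analysis in either document: "ISI at baseline, at post-op, 7 days, 1, 3, and 6 months. RMANOVA will be used". Baseline is one of the listed responses. Item 7, for IPSS change scores, adds models with the baseline score as a covariate; item 14 does not. The section 7 endpoints use the PP cohort and "are pre-specified but are not intended to support product labeling".

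Incontinence also enters by other routes:
- Protocol section 8 defines urinary incontinence as men who needed no pads before treatment and "require more than 1 incontinence pad per day post-treatment".
- The Table 5 footnote in section 2.30.1 counts "persistent ejaculatory dysfunction, erectile dysfunction or urinary incontinence" among Grade 1 events.
- Under section 4.5.3, the "summary of adverse events in the trial will be analyzed using this analysis population, divided into groups according to actual treatment received".

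Men who leak at baseline can enrol. Exclusion 13 removes only stress incontinence that requires treatment or daily pad or device use.

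**The concern.** After surgery the mean ISI can move for two opposite reasons. Men whose leakage came from obstruction may become dry, and men who were dry may start to leak. A mean over the whole cohort adds the two. A difference between arms could then come from either source, and a real difference in new leakage could be diluted by the men who leaked before, or offset by better relief in the same arm.

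At stake is whether a reader can see how many previously dry men leak after each procedure. That is the distinction for which the protocol says the ISI is collected.

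**Working it through.** The plan states no figure for the ISI, so there is none to reproduce. Every rate and score below is an assumption.

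**Sample size.** 156 evaluable men (protocol section 4.4) split 2:1 gives 104 Aquablation and 52 TURP.

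**1. Offsetting by hand.** Assume 30% leak at baseline with score 4, new leaks score 2, new leakage is 15% v 5% of dry men, and relief is 61.7% v 50%.

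Mean change = (share dry × new rate × 2) − (share leaking × 4 × relief).
- Aquablation: 0.7 × 0.15 × 2 − 0.3 × 4 × 0.617 = 0.21 − 0.74 = −0.53
- TURP: 0.7 × 0.05 × 2 − 0.3 × 4 × 0.50 = 0.07 − 0.60 = −0.53

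New leakage is three times as common in one arm, yet the mean changes are equal. This needs unequal relief.

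**2. Dilution when relief is equal.** Assume scores of 2 to 6 when incontinent (mean 4), 80% relief in both arms, status constant after surgery, and new leakage of 20% v 5%.

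Arm difference in post-surgery mean = share dry × 0.15 × 4.
- Baseline leakage 10/20/30%: 0.54/0.48/0.42 points
- The six-response mean (baseline plus five visits) differs by 5/6 of that: 0.45/0.40/0.35 points

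The second line is what the arm effect in the next step tests. The signal shrinks but does not vanish.

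**3. Simulated power.** 20,000 trials per scenario, two-sided 0.05. The repeated-measures arm effect is a t-test on each man's six-response mean. The new-leakage test is a pooled z-test among men dry at baseline. Entries are for baseline leakage of 10/20/30%.

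| New leakage | Worse arm | Repeated measures | New-leakage proportion |
|---|---|---|---|
| 20% v 5% | Aquablation | 55/42/31% | 71/66/58% |
| 20% v 5% | TURP | 63/49/36% | 79/74/68% |
| 15% v 5% | Aquablation | 29/21/17% | 41/36/32% |
| 15% v 5% | TURP | 38/28/21% | 53/48/44% |
| 5% v 2% | Aquablation | 6/6/5% | 5/4/3% |
| 5% v 2% | TURP | 11/9/7% | 18/18/16% |

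Under equal rates of 2%, 5% and 10%, the rejection rate is 4.0 to 5.1% for the repeated-measures test and 3.2 to 4.9% for the proportion. A post-surgery model with baseline ISI as covariate gives 58/45/34% (Aquablation worse) and 67/54/42% (TURP worse) at 20% v 5%. The covariate helps a little but does not isolate new leakage.

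**4. A signal without any new-leakage difference.** Set new leakage at 5% in both arms and relief at 90% v 50%. The repeated-measures test is significant in 14/31/48% of trials, and the new-leakage test in about 4%.

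**5. Precision of the proposed proportion.** Men dry at baseline: 104 × 0.9 ≈ 94 and 52 × 0.9 ≈ 47 at 10% baseline leakage; 104 × 0.7 ≈ 73 and 52 × 0.7 ≈ 36 at 30%. At 20% v 5%, Aquablation worse, the Wald half-width at 10% is 1.96 × √(0.20 × 0.80/93.6 + 0.05 × 0.95/46.8) = 0.102. Across 10/20/30% it is 10.2/10.9/11.6 points, and 12.3/13.0/13.9 if TURP is worse. Score intervals give 11.2/12.0/12.9 and 12.4/13.2/14.2.

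**The case against.** **No commitment is broken.** A reader might infer that the SAP contradicts a protocol endpoint. It does not. Section 2.29 describes what an instrument is for, and section 3.3 lists only visits. A baseline ISI could also serve that purpose by helping to judge whether a reported event is new. This stands: the point concerns how well the analysis fits the stated purpose.

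**Adverse events cover new incontinence.** A reader might infer that new incontinence goes unanalysed, or that mild leakage is certainly lost. Neither is supported. Section 2.30.1 documents all adverse events, persistent incontinence is a Grade 1 event, and events are summarised by treatment received. The pad-based entry in section 8 is not labelled an adverse-event threshold, although the neighbouring hematuria and retention entries are labelled as adverse events. Whether leakage needing no pad or one pad a day is counted is therefore unclear. The ISI is collected from every man at fixed visits, so a proportion from it would not depend on that reading.

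**The repeated-measures analysis is not blind.** A reader might infer that it can show nothing about incontinence. Step 3 shows otherwise: it detects net shifts. What it lacks is the number of newly leaking men and the separation from relief. Complete offsetting needs unequal relief, which no document suggests.

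**The gain is modest.** At 5% v 2% neither test has useful power, and with Aquablation worse the proportion does slightly worse. The assumed scores of 2 to 6 are not specific to mild leakage. This stands; the case for the table is that it is interpretable, not that it guarantees power.

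**The precedent is partial.** SAP item 19 already analyses "Change in categorization of subjects from obstructed to unobstructed or unobstructed to obstructed at month 6", but obstruction status was a listed protocol endpoint with numeric cut-offs. The ISI has neither, so item 19 shows only that two-way change of status is familiar to this plan.

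**Conclusion.** The point holds as an optional, low-impact improvement. Item 14 compares mean ISI between arms and combines two processes that the protocol says the ISI should help to separate. It does not give the number of newly leaking men by arm, and it can be significant from unequal relief alone.

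The mixing follows from the method and the eligibility criteria. The sizes rest on assumed ISI rates and scores, constant status after surgery, and a t-test standing in for the repeated-measures arm effect; item 14 does not say which contrast will be tested. The power figures are illustrations, not predictions for this trial. No primary or secondary conclusion changes.

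**What to change.** Add to SAP section 7, item 14:

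- By arm, at 3 months and at 6 months, n/N and the proportion of men with any incontinence on the ISI among those with none on the baseline ISI, with the difference and 95% CI from `ciBinomial`, which the SAP already names.
- Separately, the proportion resolved among men incontinent at baseline.
- The repeated-measures analysis kept as supportive, with baseline ISI as a covariate.

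Define continence by the instrument's own no-leakage category. Taking this as a score of 0 is an assumption, because the documents give no ISI scoring. Protocol section 3.3 is headed as already reported, so label the addition supplementary if ISI results are known.

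The cost is one or two sentences and one table, with no new data. The drawbacks are smaller denominators, a 95% CI half-width of about 10 to 14 points under the assumed 20% v 5%, and sensitivity to trivial leakage.

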## 8 Subgroup Analyses

Subgroup analyses of primary safety and effectiveness endpoints, as well as selected secondary endpoints, will be performed for the following subgroups:

- baseline IPSS scores of  $<20$  vs.  $\geq 20$
- baseline prostate size of  $<50\text{g}$  vs.  $\geq 50\text{g}$
- Age  $<65$  vs.  $\geq 65$  years at baseline

## 9 Pooling

Data will be pooled across sites when performing statistical analysis. The justification for pooling includes the following:

- Study sites will be following the same Protocol
- Study sites use the same device system
- Study sites follow the same instructions for use document
- Study subjects are enrolled using identical criteria across sites
- Randomization within site is designed to ensure balance within sites, minimizing site-to-site variation of treatment effect
- Frequent contact with sites and monitoring of study data

Potential heterogeneity of results will be examined. For the primary effectiveness endpoint, analysis of variance will be used to determine heterogeneity of effect sizes across site. Heterogeneity will be assumed to be present if the site  $\times$  treatment interaction p-value is  $<.05$ . Additional models may incorporate potential predictors of IPSS change scores, including baseline demographic factors (age, race), baseline IPSS scores, procedure-related variables (ablation time, resection time). If these variables do not adequately explain heterogeneity across sites, mixed models will be used that assume variation of change scores or treatment effect across sites.

For the primary safety endpoint, heterogeneity will be assessed using a Mantel-Haenzel odds ratio test or similar test. Heterogeneity will be assumed to be present if the site  $\times$  treatment interaction p-value is  $<.05$ . If evidence of non-poolability is found, baseline and procedural variables found to be different between sites will serve as predictors in a logistic or linear regression that also includes as predictors the treatment assignment, site, and site-by-treatment interaction. If these variables do not adequately explain heterogeneity across sites, mixed models will be used that assume variation of event rates across sites. Mixed models treat some factors (e.g., site ID) as a random effect and are often used in this situation.

Variation may be different across procedures. That is, variation may be smaller in A vs. T, since A is automated. Variation in IPSS change scores and the primary safety endpoint across sites will therefore be examined within procedure.

